7.5.4 Extra-pelvic Relapse Free Survival (EPRFS)

Extra-pelvic relapse free survival (EPRFS) is defined as the date from randomization (as recorded in Centralized Randomization File) to the documented reappearance of disease provided that this recurrence is outside of pelvic (as recorded in Extra-pelvic Recurrence Section in Recurrence Report). Patients found to have more advanced stages of cervical cancer on intraoperative findings consistent with extra-pelvic disease will be considered to have extra-pelvic disease relapse as of the date of the surgical procedure. Patients who relapse in pelvic field will be censored at the time of first documented pelvic relapse (as recorded in Pelvic Recurrence Section in Recurrence Report). Patients who die before any relapse or alive without recurrence will be censored at the date of death (as recorded in Death Report) or last disease assessment date (as defined in Section 7.5.1).

A summary of all intention to treat patients who have extra-pelvic recurrence and sites of recurrences will be displayed (Table 24). The Kaplan-Meier plot of EPRFS will be presented in each of the treatment arms (Figure 3).

The Kaplan-Meier estimate for the 3 year EPRFS will be provided for each treatment arm and the difference between the two treatment arms in EPRFS will be tested using a two-sided log-rank test stratified by the stratification factors at randomization as listed in Section 7.5.3. Hazard ratio with two-sided 95% C.I. of simple hysterectomy over radical hysterectomy will also be computed based on the Cox model adjusting for the same stratification factors at randomization. Subset analyses by each level of the baseline factors listed in Section 5.1.2 and sensitivity analysis based on per-protocol patients will also be performed (Table 27).

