Data from the recent 24th annual International Federation of Gynecology and Obstetrics (FIGO) report indicates that the 5-year stage-specific overall survivals of patients with stage IA2 squamous carcinoma were 99.1% (97.1% for adenocarcinoma) and for stage IB1 squamous carcinoma were 92.3% (91.8% for adenocarcinoma) [FIGO Annual Report, 2009]. The FIGO report emphasizes that from an international perspective, extensive practice variation occurs in managing patients with micro-invasive disease. Overall, 75% of patients were treated with surgery alone. Among these patients, one-third underwent conization, one-third simple hysterectomy (with or without lymphadenectomy) and one-third radical hysterectomy (again with or without lymphadenectomy). The remaining 25% of patients received some form of adjuvant therapy. Overall, 20% of patients underwent lymph node removal, presumably when lymphovascular involvement was detected on the conization specimen [FIGO Annual Report, 2009]. The major reason for such discrepant practices is the lack of high-quality evidence upon which clinicians can base their decisions and advice to these women. There is a need to standardize treatments and potentially identify the patient and disease specifics associated with advantages with radical or more limited surgical approaches.

There are no studies comparing the efficacy and morbidity of simple hysterectomy to that of radical hysterectomy in patients with early-stage disease. However, as the purpose of removing the parametria at the time of the hysterectomy is to ensure safe and wide margins around the cervical tumour and/or to remove potential spread to the parametrial lymph nodes and, as will be described below, the occurrence of disease in these locations is essentially nonexistent in patients with low-risk disease, important advantages may be associated with a simple hysterectomy. This premise provides the foundation for this trial.

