2.2.2 Outcomes Justifying Testing of Less Radical Approaches in Stage IB1

Fewer data are available regarding the safety of conservative treatment for the subset of patients with early-stage IB1 disease, defined as a tumour measuring less than 2 cm. In a retrospective study of 842 patients, Covens questioned the necessity of the parametrectomy based on observing a rate of parametrial extension of 0.6% and 2 and 5-year recurrence-free survivals of 98% and 96% in patients with low-risk features (tumour < 2cm, depth of stromal invasion < 10mm and negative pelvic nodes) [Covens 2002]. Wright conducted a retrospective review of 594 patients who underwent a radical hysterectomy; 0.4% of patients with lesions measuring < 2cm, negative nodes and no LVSI had parametrial spread and their recurrence rate was 0.7% [Wright 2007]. The authors concluded that simple hysterectomy in combination with pelvic lymphadenectomy may be adequate treatment for these patients. In a similar study plus literature review of 799 patients, only 0.63% of those with low-risk features had parametrial spread [Stegeman 2007]. Further supporting data include:

- In a retrospective analysis of 120 patients by Steed, no patients with negative nodes had parametrial infiltration. Parametrial infiltration was associated with tumour size (3 vs. 2 cm) and depth of stromal invasion [Steed 2006].
- In a retrospective analysis of 83 patients by Kinney, no parametrial node metastases were seen in those with lesions measuring < 2cm in diameter and negative LVSI. Only 4 patients had pelvic node metastasis (4.8%), and the 5-year survival was 97.6% [Kinney 1995].
- In a retrospective analysis of 136 patients by Frumovitz, no patients with tumours measuring < 2cm with negative LVSI had parametrial infiltration [Frumovitz 2009]. This group is now prospectively testing conservative surgery for patients with tumours < 2 cm who are LVSI negative.
- Coutant has reported that tumour size < 2cm and absence of LVSI are the most relevant preoperative factors that predict for parametrial infiltration [Coutant 2009].

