7.5.2 Pelvic Recurrence Rate at 3 Years by Subsets

For each level of the following baseline factors baseline factors, the pelvic recurrence rate at 3 years in each of the treatment arms and the difference of 3-year recurrence rate between two arms with one-sided 95% C.I. will be displayed (**Table 25**).

- Age: ≤ 65 , > 65
- Race: White, Asian, Others
- Intended use of SN mapping: yes, no
- Histological stage: IA2, IB1
- Histological type: squamous, adenocarcinoma/adenosquamous
- Tumour grade: 1-2, 3, not assessable

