	No	**	***	**	***	*** (***-***)	0.**
Histologic stage	IA2	**	***	**	***	*** (***-***)	0.**
	IB1	**	***	**	***	*** (***-***)	0.**
Histologic type	Squamous	**	***	**	***	*** (***-***)	0.**
	Adenocarcinoma/ adenosquamous	**	***	**	***	*** (***-***)	0.**
Race	1-2	**	***	**	***	*** (***-***)	0.**
	3	**	***	**	***	*** (***-***)	0.**
	Not assessable	**	***	**	***	*** (***-***)	0.**
Per-protocol patients	All	**	***	**	***	*** (***-***)	0.**

(1) Between simple hysterectomy and radical hysterectomy;

(2) From two-side log-rank test stratified by stratification factors except corparative group at randomization.

Figure 4: Kaplan-Meier Curves for Relapse Free Survival

[figure not shown]

Table 28: Analysis for Relapse Free Survival (RFS)

Factors	Value	Simple Hysterectomy		Radical Hysterectomy		Hazard Ratio ⁽¹⁾ (Two-sided 95% C.I.)	P-value ⁽²⁾
		N	3-year RFS	N	3-year RFS		
Intention-to-treat patients	All	**	***	**	***	*** (***-***)	0.**
Age	≤65	**	***	**	***	*** (***-***)	0.**
	>65	**	***	**	***	*** (***-***)	0.**
Race	White	**	***	**	***	*** (***-***)	0.**
	Asian	**	***	**	***	*** (***-***)	0.**
	Others	**	***	**	***	*** (***-***)	0.**
Intended use of sentinel node mapping	Yes	**	***	**	***	*** (***-***)	0.**
	No	**	***	**	***	*** (***-***)	0.**
Histologic stage	IA2	**	***	**	***	*** (***-***)	0.**
	IB1	**	***	**	***	*** (***-***)	0.**
Histologic type	Squamous	**	***	**	***	*** (***-***)	0.**
	Adenocarcinoma/ adenosquamous	**	***	**	***	*** (***-***)	0.**
Race	1-2	**	***	**	***	*** (***-***)	0.**
	3	**	***	**	***	*** (***-***)	0.**
	Not assessable	**	***	**	***	*** (***-***)	0.**
Per-protocol patients	All	**	***	**	***	*** (***-***)	0.**

(1) Between simple hysterectomy and radical hysterectomy;

(2) From two-side log-rank test stratified by stratification factors except corparative group at randomization.

Table 29: Summary of Events for Analyses of Survival

Dataset: All Intention-To-Treat Patients			
	Number of patients (%)		
	Simple Hysterectomy N=***	Radical Hysterectomy N=***	Total N=***
Patients who died			
No	**(**)	**(**)	**(**)
Yes	** (**)	** (**)	** (**)
Cause of death			
Cervix cancer only	**(**)	**(**)	**(**)
Other primary malignancy	**(**)	**(**)	**(**)
...	**(**)	**(**)	**(**)
Patients who had an event for OS	**(**)	**(**)	**(**)
Patients who were censored for OS	** (**)	** (**)	** (**)
Patients who were alive	**(**)	**(**)	**(**)

Figure 5: Kaplan-Meier Curves for Overall Survival

[figure not shown]

Table 30: Analysis for Overall Survival (OS)

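### SAP Tables 27, 28 and 30 give a log-rank p-value in each of 14 subset levels but no interaction test, so they do not test whether the treatment effect differs between subsets

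*SAP*

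**What the plan says.** After the overall comparison for extra-pelvic relapse-free survival (EPRFS), SAP 7.5.4 plans: "Subset analyses by each level of the baseline factors listed in Section 5.1.2 and sensitivity analysis based on per-protocol patients will also be performed". The SAP has no Section 5.1.2 (its Section 5 is sample size and power), and Section 5.1.2 of the protocol is an eligibility criterion. The list meant is evidently the one in SAP 7.5.2, which 7.5.3 cites correctly. It contains age (up to 65, over 65), "Race: White, Asian, Others", "Intended use of SN mapping: yes, no", "Histological stage: IA2, IB1", "Histological type: squamous, adenocarcinoma/adenosquamous", and tumour grade in three levels.

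SAP 7.5.5 and 7.5.6 apply similar methods to relapse-free survival (RFS) and overall survival (OS). The shells of Tables 27, 28 and 30 have a p-value cell in every subset row, and the note to that column reads "From two-side log-rank test stratified by stratification factors except corparative group at randomization". In these three shells the grade rows are labelled Race; I read them as grade from their levels.

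The SAP handles its pelvic endpoints differently. For pelvic relapse-free survival (PRFS), 7.5.3 specifies an unstratified hazard ratio per level with a one-sided upper limit (Table 26) and no p-value. Table 25 likewise shows only a difference and its upper limit. The only interaction term in either document is treatment by time in the mixed model for patient-reported outcomes (SAP 7.8.4.2). No significance level, multiplicity adjustment or exploratory label is given for any subset.

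**The concern.** A small p-value in one level and a large one in its neighbour is not evidence that the two levels differ. That requires a test of treatment by factor, and none is planned. The background in Protocol 2.1 speaks of a need to "potentially identify the patient and disease specifics associated with advantages with radical or more limited surgical approaches", so readers will look at these tables with that question in mind and find p-values that do not answer it.

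Events are also few. SAP 2.1 reports 14 pelvic recurrences two years after accrual closed. Split over 14 levels and three endpoints, the log-rank p-values will often rest on a handful of events. Some will fall below 0.05 by chance, and nothing in the plan tells the reader how to treat them.

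**Working it through.** **1. The plan's own figures.** The documents give no error rate or power for the subsets, so this step only checks the inputs.
- Power for the primary test, 350 per arm, 4% in both arms, margin 4 points, one-sided 0.05: SE = √(2 × 0.04 × 0.96 / 350) = 0.0148; 0.04/0.0148 − 1.645 = 1.055; power 85.4%. The stated 85% reproduces.
- Hazard ratio margin: ln 0.92 / ln 0.96 = 2.04. Events for 80% power at one-sided 0.05 (Schoenfeld): 4 × (1.645 + 0.842)² / (ln 2.04)² = 48.7, so 49. Both reproduce.

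**2. Number of tests.** From SAP 7.5.2: 2 + 3 + 2 + 2 + 2 + 3 = 14 levels per table; 14 × 3 = 42 over Tables 27, 28 and 30. No subset significance level is stated, so two-sided 0.05 is assumed, to match the two-sided 95% intervals in 7.5.4.

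**3. Reference figure if the tests were independent.** 1 − 0.95¹⁴ = 51.2% per table; 1 − 0.95⁴² = 88.4% over three tables; 42 × 0.05 = 2.1 expected false positives. The tests are not independent, because the same women appear under every factor and the endpoints share events.

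**4. Simulation with no treatment effect.** Subset shares and event counts outside the pelvis are not in the documents, so they are assumed. Both simulations use 700 women and unstratified tests.

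| Assumptions | At least one p<0.05, per table | Over three tables | Mean false positives |
|---|---|---|---|
| Follow-up 3-10 years, 1% three-year rate per relapse type | 34% (RFS) | 54% | 1.56 |
| Same, 2% rate | 37% (RFS) | 62% | 1.88 |
| 7-49 extra-pelvic relapses, 21-98 any relapse, 13-59 deaths; skewed or even subset shares | 18-35% | 52-67% | 1.2-1.8 |

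The first two rows assume 6% over 65, race 60/25/15, mapping 40/60, IB1 90%, histology 60/40 and grade 60/15/25. In the third row the skewed shares are close to these, and the even shares split each factor equally.

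**5. Small levels.** With balanced arms, d events in a level and x of them in one arm, z = |x − d/2| / √(d/4).
- d = 3: the most extreme split, 3-0, gives z = 1.5/0.866 = 1.73. Significance cannot be reached.
- d = 4: a 4-0 split gives z = 2/1 = 2.0, p = 0.046. Its chance under the null is 2 × 0.5⁴ = 12.5%, which is 2.5 times the nominal 5%.

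**6. Stratification inside levels.** The four factors in the note form 2 × 2 × 2 × 3 = 24 strata. Within the five age and race levels all 24 apply. In the other nine levels one factor is constant, leaving 12 strata (mapping, stage, histology) or 8 (grade). A stratum informs the test only if it has an event while both arms are at risk. A smaller simulation (600 trials per scenario) gave similar false-positive rates with and without stratification. The mismatch with 7.5.3 therefore costs information and consistency; it does not inflate the error rate.

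**7. After the change.** One interaction test per factor is 6 per table and 18 over three tables. If independent: 1 − 0.95⁶ = 26.5%, 1 − 0.95¹⁸ = 60.3%, and 18 × 0.05 = 0.9 expected false positives.

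Power for a two-level factor with equal halves and D events: the SE of the log ratio of hazard ratios is √(2 × 4/(D/2)). For D = 49 this is 0.571. A ratio of 2 then has power Φ(0.693/0.571 − 1.96) = 23%, and a ratio of 3 has 49%. For D = 21 the figures are 12% and 24%.

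**The case against.** The strongest reply is that nothing is decided by these p-values. The only rules for claiming non-inferiority are in SAP 7.5.1 and 7.5.3, and neither document lists a subgroup objective. The sentence quoted from Protocol 2.1 describes a general need arising from varied practice. For pelvic control, the outcome that matters most when choosing the smaller operation, Tables 25 and 26 already show subsets without p-values. All of this stands, and it limits the point to three other secondary endpoints.

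Four stronger readings are tempting, and the documents do not support them.

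- A reader might infer that a false positive is likely in each table. The per-table range is 18-37%. It passes one half only when the three endpoints are pooled, and then only under assumed inputs.
- A reader might infer that deleting the p-values removes this risk. It does not. A two-sided 95% interval that excludes 1 is nearly the same event as p<0.05, and the intervals stay.
- A reader might infer that the smallest levels are the main source of chance findings. With three or fewer events and balanced arms, the test cannot reach 0.05. The distortion begins at four events.
- A reader might infer that leaving baseline lymphovascular invasion (LVSI) off the subset list is an error. Protocol 2.2.2 reports one study in which "tumour size < 2cm and absence of LVSI are the most relevant preoperative factors that predict for parametrial infiltration", but that concerns parametrial infiltration and not recurrence. Protocol 2.2.1 also cites reviews that found no link between LVSI and nodal risk, women are eligible with or without it, and it is not a stratification factor. Adding it is a preference, and it would add tests.

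**Conclusion.** The point holds as a defect in how three secondary endpoints are to be reported. The plan yields 42 within-level p-values, no test of whether the effect differs between levels, and no label to guide the reader. Its within-level stratification also departs from the unstratified subset analysis in 7.5.3, and its cross-reference has no target in the SAP.

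Under no treatment effect, the chance of at least one p<0.05 is roughly 18-37% per table and 52-67% over the three, with 1.2-1.9 false positives on average. These figures rest on assumed subset shares and event counts and on a nominal two-sided 0.05 level. The counts of levels and tests, the absence of an interaction test and the 12.5% attained level with four events in balanced arms do not depend on the assumed shares or counts. The primary and PRFS conclusions are unaffected. The change is worth making because it is cheap and puts the right question to the data.

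**What to change.** - In Tables 27, 28 and 30, delete the p-value in each subset row. Keep a hazard ratio and interval per level, stated to be unstratified as in 7.5.3.
- Add one treatment-by-factor interaction test per factor to these three tables.
- In 7.5.4 to 7.5.6, state that all subset results are exploratory and unadjusted for multiplicity, that interaction power is low with the events expected, and that the per-level intervals are not to be read as tests.
- Point 7.5.4 to Section 7.5.2, and correct the label of the grade rows in the three shells.

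The cost is SAP wording and table columns; no new data are needed. The drawback is low power: about 23% for a two-fold ratio of hazard ratios even with 49 events. The simulated false-positive rate should not be presented as removed by this change: 18 interaction tests still carry 0.9 expected false positives at the nominal level, and the intervals remain.

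Adding baseline LVSI as a subset and extending interaction tests to Tables 25 and 26 are optional. The latter would bring the count to 6 × 5 = 30, with a chance of at least one p<0.05 of 1 − 0.95³⁰ = 79% if independent.

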7.5.5 Relapse Free Survival (RFS)

Relapse free survival (RFS) is defined as the date from randomization (as recorded in Centralized Randomization File) to the first time when either a pelvic or extra-pelvic recurrence is documented. Patients who die before any recurrence or alive without recurrence will be censored at the date of death (as recorded in Death Report) or last disease assessment date (as defined in Section 7.5.1).

The analysis of RFS will be done using a similar methodology for EPRFS (Table 24, Figure 4, and Table 28).

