1.2 Secondary Objectives

- To compare the two treatment arms with respect to:
 - Pelvic relapse-free survival
 - Extra pelvic relapse-free survival
 - Relapse-free survival (any site)
 - Overall survival
 - Treatment-related adverse events
 - Patient Reported Outcomes including global quality of life and measures of sexual health
 - Cost-effectiveness and cost-utility

- To observe rates of the following in this patient population:
 - Sentinel node detection
 - Parametrial involvement
 - Involvement of surgical margins
 - Pelvic node involvement

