10.1 Definitions

The major parameters of outcome are pelvic recurrence rate at 3 years, pelvic and extra-pelvic relapse-free survival and overall survival.

- 10.1.1 Pelvic recurrence rate at 3 years is defined as a probability of pelvic recurrence within 3 years from randomization. A pelvic recurrence is defined as a recurrence within the pelvis, below the pelvic brim and inferior to the L4-L5 vertebral level. Pelvic recurrences will include disease recurrence in the vaginal vault, parametrium and pelvic lymph nodes (including the common iliac nodes).
- 10.1.2 Pelvic Relapse-Free Survival is defined as the date from randomization to the date of first documented reappearance (recurrence) of disease provided that this recurrence is in the pelvis.
- 10.1.3 Extra-Pelvic Relapse-Free Survival is defined as the date from randomization to the date of first documented reappearance (recurrence) of disease provided that this recurrence is outside of the pelvis. An extra-pelvic recurrence is defined as a recurrence outside of the pelvis, including above the pelvic brim and/or superior to the L4-L5 vertebral level. Extra-pelvic recurrences will include the para-aortic lymph nodes.
- 10.1.4 Recurrence is defined as new clinical, imaging or cellular/tissue-based specimen evidence of cervical cancer since study entry.
- 10.1.5 Site of First Recurrence (i.e. para-aortic or supraclavicular lymph nodes, lung, liver, bone, etc.) will be documented.
- 10.1.6 Overall Survival is defined as the time from randomization until death from any cause. For living patients, the date corresponding to the most recent date of patient contact (regardless of whether this date is protocol required) will be used.

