7.5 Efficacy

7.5.1 Pelvic Recurrence Rate at 3 Years

The pelvic recurrence rate at 3 years, the primary endpoint of the study, will be estimated by 1-the Kaplan-Meier estimate for the probability of pelvic relapse free survival (PRFS) at 3 years, where PRFS is defined as the time from randomization (as recorded in Centralized Randomization File) to the time when a recurrence within the pelvic field was first documented (as recorded in Pelvic Recurrence Section in Recurrence Report). Patients found to have more advanced stages of cervical cancer on sentinel node mapping, pelvic node dissection or other intraoperative findings consistent with pelvic disease will be considered to have pelvic disease relapse as of the date of the surgical procedure. Patients who have a relapse outside of the pelvic

field documented or die before the documentation of a pelvic relapse will be censored at the time of first documented extra-pelvic relapse (as recorded in Extra-pelvic Recurrence Section in Recurrence Report) or death (as recorded in Death Report). The pelvic relapse free survival of patients who are alive without any relapse will be censored at the last disease assessment (randomization date, date of surgery in Surgery Report, date of physical exam in Surgery Report, date of last contact in Adjuvant Treatment Report, date of Attendance/Last Contact in Follow-up Report and Short Follow-up Report, date of last patient contact in Lost to Follow Up Report, date of consent withdrawal in Withdrawal of Consent Report, whichever comes the last).

A summary of patients who have pelvic recurrence and sites of the pelvic recurrence will be provided (**Table 24**).

The pelvic recurrence rate at 3 years will be calculated for each arm as well as the difference in pelvic recurrence rates at 3 years between simple hysterectomy to radical hysterectomy. The upper limit of a one-sided 95% confidence interval for the difference will be calculated based on the Greenwood estimate for the variance of the estimated 3-year PRFS (**Table 25**). The non-inferiority of simple hysterectomy to radical hysterectomy will be claimed when this upper limit is lower than or equal to 4%.

The primary analysis will be performed on all intention-to-treat patients and a sensitive analysis will additionally be conducted for all per-protocol patients defined in Section 6 based on arms they are treated (**Table 25**).

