Table 24: Summary of Events for Analyses of Recurrence

Dataset: All Intention-To-Treat Patients			
	Number of patients (%)		
	Simple Hysterectomy N = ***	Radical Hysterectomy N = ***	Total N=***
Patients who had pelvic recurrence			
No	** (***)	** (***)	** (***)
Yes	** (**)	** (**)	** (**)
Site of pelvic recurrence			
Vaginal Vault	** (***)	** (***)	** (***)
Parametrium	** (***)	** (***)	** (***)
Pelvic Lymph Nodes	** (***)	** (***)	** (***)
Other	** (***)	** (***)	** (***)
Patients who had extra-pelvic recurrence			
No	** (***)	** (***)	** (***)
Yes	** (**)	** (**)	** (**)
Site of extra-pelvic recurrence			
Para-aortic lymph node	** (***)	** (***)	** (***)
Bone	** (***)	** (***)	** (***)
Brain	** (***)	** (***)	** (***)
...	** (***)	** (***)	** (***)
Patients who had both pelvic and extra-pelvic recurrences	** (***)	** (***)	** (***)
Patients who had either pelvic or extra-pelvic recurrences	** (***)	** (***)	** (***)
Patients who had more advanced stages of cervical cancer on sentinel node mapping, pelvic node dissection or other intraoperative findings	** (***)	** (***)	** (***)
Patients who died			
No	** (***)	** (***)	** (***)
Yes	** (**)	** (**)	** (**)
Cause of death			
Cervix cancer only	** (***)	** (***)	** (***)
Other primary malignancy	** (***)	** (***)	** (***)
...	** (***)	** (***)	** (***)
Patients who had an event for PRFS	** (***)	** (***)	** (***)
Patients who were censored for PRFS	** (**)	** (**)	** (**)
Patients who had extra-pelvic recurrence as the first recurrence	** (***)	** (***)	** (***)
Patients who died without recurrence	** (**)	** (**)	** (**)
Patients who were alive without recurrence	** (**)	** (**)	** (**)
Patients who had an event for EPRFS	** (***)	** (***)	** (***)
Patients who were censored for EPRFS	** (**)	** (**)	** (**)
Patients who had pelvic recurrence as the first recurrence	** (***)	** (***)	** (***)
Patients who died without recurrence	** (**)	** (**)	** (**)
Patients who were alive without recurrence	** (**)	** (**)	** (**)
Patients who had an event for RFS	** (***)	** (***)	** (***)
Patients who were censored for RFS	** (**)	** (**)	** (**)
Patients who died without recurrence	** (***)	** (***)	** (***)
Patients who were alive without recurrence	** (**)	** (**)	** (**)

Table 25: Analysis for Pelvic Recurrence Rate at 3 Years

Factors	Value	Simple Hysterectomy		Radical Hysterectomy		Difference** (%) (Upper limit of one-sided 95% C.I.)
		N	Rate*	N	Rate*	

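### SAP 7.5.5 does not carry the surgery-date event rule into any-site relapse-free survival, so as written RFS is not the composite of PRFS and EPRFS

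*SAP*

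**What the plan says.** SAP 7.5.1 defines the PRFS event by the Recurrence Report and then adds a separate rule. Women found at node mapping, node dissection or otherwise during the operation to have more advanced pelvic disease "will be considered to have pelvic disease relapse as of the date of the surgical procedure". SAP 7.5.3 takes over this definition for PRFS. SAP 7.5.4 does the same for EPRFS: women with extra-pelvic findings at surgery "will be considered to have extra-pelvic disease relapse as of the date of the surgical procedure".

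SAP 7.5.5 runs RFS "to the first time when either a pelvic or extra-pelvic recurrence is documented" and has no such rule. On censoring it says: "Patients who die before any recurrence or alive without recurrence will be censored at the date of death" or at the last disease assessment. It cites 7.5.1 only for the date of that last assessment, and EPRFS only for the analysis: "The analysis of RFS will be done using a similar methodology for EPRFS".

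Table 24 (SAP Appendix 1) has one row for "Patients who had more advanced stages of cervical cancer on sentinel node mapping, pelvic node dissection or other intraoperative findings", apart from the rows for pelvic, extra-pelvic, both and either recurrence.

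Protocol 1.2 lists any-site RFS as a secondary endpoint, but Protocol 10.1 and 14.2 do not define it. SAP 7.5.5 is therefore its only definition.

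**The concern.** RFS at any site should contain every event of its pelvic and extra-pelvic components. The SAP states the surgery-date rule in both component sections and leaves it out of the section that combines them. On the literal text, a woman upstaged at surgery without later documented recurrence has relapsed for PRFS or EPRFS, yet counts as alive or dead without recurrence for RFS. A woman upstaged at surgery who does recur later is an event in both, but at a later date for RFS.

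Tables 26 and 28 would then rest on different event definitions. A reader comparing them could find fewer relapses at any site than in the pelvis alone. Two analysts working from this SAP could also derive different RFS event counts, and so different hazard ratios and log-rank p-values for Table 28.

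**Working it through.** **The plan's own figures.** The documents give no planning figure for RFS. The nearest is the power of the primary comparison, which reproduces: Φ(0.04/√(2×0.04×0.96/350) − 1.645) = 85.4%, against the stated 85%. It is not in dispute and does not bear on this point.

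**Order of the endpoints.** PRFS and RFS are both meant to end at the first of pelvic relapse, extra-pelvic relapse, death or last assessment. They differ in that PRFS censors an extra-pelvic first relapse and RFS counts it. Under one shared event rule the risk sets are the same, and RFS has at least as many events at each time. Its Kaplan-Meier curve then cannot lie above the PRFS curve. Without the rule in RFS, this guarantee is lost.

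**Inputs for an illustration.**
- N = 700, the planned sample size (Protocol 14.3).
- P = 14 documented pelvic-first recurrences, the number SAP 2.1 reports two years after accrual ended. The documents do not say whether upstaged women are among them; here they are assumed not to be.
- U = women upstaged to pelvic disease with no later documented recurrence. Assumed 4, 7, 14 or 34, that is 0.5%, 1%, 2% or 4.8% of 700 (3.5 and 33.6 rounded up). The 0.5% and 4.8% are nodal metastasis rates in Protocol 2.2.1; the others lie between.
- X = extra-pelvic-first recurrences. Assumed 7 or 14 (1% or 2%).
- Everyone else is followed beyond 3 years, and nobody is upstaged with extra-pelvic disease only.

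**Formulas.**
- PRFS events = P + U
- RFS events as written = P + X
- RFS events with the rule = P + U + X
- 3-year estimate ≈ 1 − events/700. Kaplan-Meier estimates on the constructed data agree to one decimal.

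| U | X | PRFS: events, 3-year | RFS as written | RFS with the rule |
|---|---|---|---|---|
| 4 | 14 | 18, 97.4% | 28, 96.0% | 32, 95.4% |
| 7 | 7 | 21, 97.0% | 21, 97.0% | 28, 96.0% |
| 14 | 7 | 28, 96.0% | 21, 97.0% | 35, 95.0% |
| 34 | 7 | 48, 93.1% | 21, 97.0% | 55, 92.1% |

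For example, with U = 34 and X = 7: 1 − 48/700 = 93.1%, 1 − 21/700 = 97.0%, 1 − 55/700 = 92.1%. As written, RFS has fewer events than PRFS exactly when U > X. In every row it misses U events. With the rule added, RFS is never above PRFS.

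**The case against.** The strongest reply is that the SAP already implies the composite. Sections 7.5.1 and 7.5.4 deem upstaged women to have relapsed, and 7.5.5 can be read as taking the earlier of the two events just defined. It names no case report form for the RFS event, so it does not expressly limit the event to the Recurrence Report. Protocol 10.1.4 is broad: "Recurrence is defined as new clinical, imaging or cellular/tissue-based specimen evidence of cervical cancer since study entry". Surgery follows randomization, so operative findings could fit. Table 24 also has no line that treats upstaged women as censored for RFS. This reading is available and may be what was intended. But if it went without saying, the explicit sentences in 7.5.1 and 7.5.4 would be unnecessary, and Table 24 would not keep upstaging apart from recurrence. Two readings remain, and the literal one breaks the composite.

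The objection to the size stands in full. Nodal rates are at best an upper proxy for U. Section 7.5.1 speaks of more advanced stages, while Protocol 2.3 notes that nodal status is not part of FIGO staging. Protocol 8.2 restricts frozen section of sentinel nodes, and the SAP does not settle whether nodes found positive only on final pathology count. The background rates also vary widely: below 5% for low-risk disease (Protocol 2.1.1) and 8.3% in a prospective simple-hysterectomy series (2.2.3), but also 0.5%, 1.5%, 0 of 92 and 0 of 51 in mainly IA2 or microinvasive series (2.2.1). U could be close to zero.

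A reader might infer that RFS will look better than PRFS. The documents do not support that, because it needs U > X and they give neither. A reader might also add upstaged women to the 4% design rate to project PRFS. That is not supported either: the documents do not say that the 4% excludes surgery-date events, and only 14 pelvic recurrences had been seen, 14/700 = 2% of the planned number.

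**Conclusion.** The omission is real and should be corrected. As written, RFS leaves out women upstaged at surgery without later documented recurrence, although PRFS or EPRFS counts them, so it is not the composite of the two. 3-year RFS could exceed 3-year PRFS if U > X; otherwise the order holds but the events are still missing. In the illustration the gap between the two RFS readings is U/700: 0.6 points at U = 4, 2.0 at U = 14 and 4.9 at U = 34. All of these rest on assumed U, X and P.

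The reach is limited to a secondary endpoint: the RFS rows of Table 24, Figure 4 and Table 28, essentially for the intention-to-treat set. SAP section 6 removes women upstaged with pelvic disease from the per-protocol set, so they cannot cause the mismatch there. It would be wrong to infer that the primary 3-year comparison or the PRFS non-inferiority test is affected, since both use the definition in 7.5.1. RFS itself has no non-inferiority margin. Nor do the documents show a bias between arms: they give no upstaging rates by arm, so no direction can be stated for the RFS hazard ratio.

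**What to change.** In SAP 7.5.5, define the RFS event as the earlier of the PRFS event (7.5.1) and the EPRFS event (7.5.4), including the surgery-date events in both. State that any analysis that drops the surgery-date rule drops it from PRFS, EPRFS and RFS together. This should be settled before RFS is derived.

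The cost is one sentence and one derivation, with no new data. The downside is that the reported 3-year RFS may be slightly less favourable, by about the proportion of women upstaged at surgery without later documented recurrence.
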